## 9.2 Preliminary studies:

There are currently four articles in the literature that studied the role of glucagon during colonoscopy. Two studies demonstrated faster cecum intubation rate and decreased overall procedure time with no change in adenoma detection rate with glucagon therapy while the other two studies demonstrated no effect. All studies were limited by a small sample size and no study determined the effect of glucagon therapy on blood sugar levels at the end of the procedure.

## 10.0 Sample Size and Eligibility

### 10.1 Number of subjects that will be enrolled at UCSF and affiliated institutions:

200

### 10.2 Total number of subjects that will be enrolled at all sites (Help Text updated 9/13):

200

### 10.3 Estimated number of people that you will need to consent and screen here (but not necessarily enroll) to get the needed subjects:

300

### 10.4 Explain how and why the number of subjects was chosen (Help Text updated 9/13):

We base our sample size calculation on the results of the recent randomized control trial comparing glucagon versus placebo prior to colonoscopy. In the study, the mean cecum intubation time was 294 seconds in the glucagon group and 370 seconds in the placebo group with a standard deviation of 140 seconds. Using a power of 0.9 and an  $\alpha$  of 0.05, a sample size of 67 participants in each study arm will be needed for this study.

### 10.5 \* Eligible age range(s):

- 0-6 years
- 7-12 years
- 13-17 years
- 18+ years

### 10.6 Inclusion criteria:

Any subject who has already been already cleared for and scheduled to undergo colonoscopy.

### 10.7 Exclusion criteria:

- 1) Refusal to give informed consent.
- 2) Age < 18 or >70.
- 3) Prior intra-abdominal surgery
- 4) Diabetes
- 5) Pheochromocytoma
- 6) Insulinoma
- 7) Liver disease (Child-Pugh Score >6)
- 8) Pregnancy

**10.8 There are inclusion or exclusion criteria based on gender, race or ethnicity:**

Yes  No

If **yes**, please explain the nature and rationale for the restrictions:

**11.0 Drugs and Devices**

**11.1 \* Investigational drugs or biologics will be used OR approved drugs or biologics will be studied under this application:**

Yes  No

**11.2 \* Investigational medical devices or in vitro diagnostics will be used OR approved medical devices or in vitro diagnostics will be studied under this application:**

Yes  No

**11.3 \* A Non-Significant Risk (NSR) determination is being requested for an investigational device:**

Yes  No

**11.4 Verification of IND/IDE numbers: If the sponsor’s protocol does not list the IND/IDE number, you must submit documentation from the sponsor or FDA identifying the IND/IDE number for this study. Attach this documentation in the Other Study Documents section of the Initial Review Submission Packet.**

**12.0 Study Drug Details**

**12.1 List the drugs or biologics that will be studied:**

View Details	Drug Name	FDA Approved	A new drug or a new use of approved drug:	IND Number
	Trade Drug Name: GLUCAGON Generic Drug Name: GLUCAGON HYDROCHLORIDE Investigational Drug Name:	Yes	No	
	Trade Drug Name:	GLUCAGON		
	Generic Drug Name:	GLUCAGON HYDROCHLORIDE		
	Investigational Drug Name:			
	Identify the name of the manufacturer or source of investigational drug/biologic:			
	Is the drug supplied at no cost?	No		
	Is the Drug FDA Approved:	Yes		
	Is this a new drug or a new use of an already approved drug	No		

Is an IND necessary	No
IND Number	
Who holds the IND:	N/A
IND details:	
If FDA Approved and an IND is not required, Please provide a rationale for exemption:	Glucagon is already regularly given by gastroenterologists prior to endoscopic procedures (ERCP, EUS and colonoscopy) to decrease spasms in the GI tract. Its use before colonoscopies is variable amongst gastroenterologists given data in the literature is conflicting regarding its benefits. Given, glucagon's regular use as an indication prior to colonoscopy in the field, we do not feel that glucagon requires an IND.
Are you currently using this IND in another research project?	No
If yes, list the IRB Number(s):	
Will the investigational pharmacy be dispensing?	No
If the source is not a FDA licensed facility, provide details regarding the purity, quality, stability and sterility of the investigational drug /biologic:	

## 13.0 Other Approvals and Registrations

### 13.1 \* Do any study activities take place on patient care units:

Yes  No

If **Yes**, attach a letter of support for the study from the involved patient care manager(s).

### 13.2 \* Does your protocol involve any radiation exposure to patients/subjects? The UCSF Radiation Safety Committee requires review of your protocol if it includes administration of radiation as part of standard of care OR research exposures:

Yes  No

### 13.3 \* This study may generate genetic data that may be broadly shared (e.g. submitted to NIH for Genome-Wide Association Studies (GWAS) in dbGaP, TCGA, etc):

Yes  No

### 13.4 \* This study involves administration of vaccines produced using recombinant DNA technologies to human subjects:

Yes  No

### 13.5 \* This study involves human gene transfer (NOTE: Requires NIH Recombinant DNA Advisory Committee (RAC) review prior to CHR approval):

Yes  No

### 13.6 This study involves other regulated materials and requires approval and/or authorization from the

**following regulatory committees:**

Institutional Biological Safety Committee (IBC)

Specify BUA #:

Institutional Animal Care and Use Committee (IACUC)

Specify IACUC #:

Radiation Safety Committee

Specify RUA #:

Radioactive Drug Research Committee (RDRC)

Specify RDRC #:

Controlled Substances

## 14.0 Procedures

**14.1 \* Procedures/Methods (Help Text updated 9/13) For clinical research list all study procedures, test and treatments required for this study, including when and how often they will be performed. If there are no clinical procedures, describe the Methods:**

1. We will create 400 cards with either glucagon or placebo written on them in a 1:1 distribution. These cards will be shuffled and placed individually into non-descript envelopes. The envelopes will be handed to our research assistant and shuffled again and each envelope will be placed in a larger envelope serially labeled from 1-400.

2. Medical records of patients presenting for a colonoscopy at the SFGH outpatient endoscopy clinic (3D) will be reviewed for inclusion into our study. On the day of the procedure, study coordinators fluent in the patient's primary language will approach the patients prior to any procedural activity. They will be informed about the medication, the proposed study and potential medication side-effects and asked of their willingness to participate in the research study. Any questions the patients may have will be answered by the study coordinators in the patient's primary language. If the patient agrees to be part of the study, he/she will be serially assigned a study number ranging from 1-400. If the patient refuses to participate in the study, they will undergo routine colonoscopy (they may still receive glucagon outside the study since some gastroenterologists routinely prescribes glucagon prior to all colonoscopies).

3. While alone in the Med-Room, nurses will open the envelope with the patient's study number and draw up 1 mg of glucagon or 1 mL of NS in a covered syringe preventing visualization of syringe content. Glucagon is reconstituted in 1mL of normal saline therefore it will be impossible to identify patient randomization even if the syringe content is visualized.

4. The patient will be given routine intravenous procedural sedation and one minute prior to the start of the colonoscopy, the nurse will be instructed to deliver the study drug.

5. The nursing staff will record, as per standard procedure during colonoscopy, the following: cecum intubation time, colonoscope withdrawal time, total procedure time, use of sedatives for the procedure. The endoscopist will rate the difficulty in scope manipulation, adequacy of visualization and the severity of spasms experienced during the colonoscopy. [name] will review the pathology results and records adenoma detection rate for each subject.

6. The patient will be discharged home according to discharge criteria already established in the outpatient GI endoscopy suite. They will be provided a questionnaire and a pre-addressed envelope prior to discharge.

7. The following day, patients will be asked by mail contact to rate pain, abdominal fullness, and willingness to accept a future colonoscopy if clinically indicated and return their questionnaire in the pre-addressed envelope provided. These will be done according to the enclosed questionnaire sheets.

If you have a procedure table, attach it to the submission with your other study documents.

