## 8.2 \* List the specific aims:

Identify whether glucagon administration during colonoscopy improves the following:

1. Cecal intubation time (time from anal insertion to reaching the cecum as noted by demonstrating the appendiceal orifice).
2. Colonoscope withdrawal time (time from withdrawing colonoscope from cecum to anus).
3. Total procedure time
4. Adenoma detection rate (i.e. the total number of polyps and adenomas per patient procedure)
5. Amount of sedatives used
6. Adequacy of visualization (graded by endoscopist)
7. Difficulty in scope manipulation (graded by endoscopist)
8. Presence and severity of spasms (graded by endoscopist)
9. Pain during procedure (graded by patients on the day after procedure)
10. Abdominal fullness (graded by patients on the day after procedure)
11. Acceptance of future colonoscopy (graded by patients on the day after procedure upon discharge from unit)

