### 16.3 Benefits to subjects:

- Yes  No

If yes, describe:

If the patient is randomized to receive glucagon, the colonoscopy may take less time, require less intravenous sedation and/or find more polyps.

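### Aim 5 records one undivided sedative amount although sedation is named before the study drug; splitting the record and adjusting for the pre-drug amount would avoid a possible loss of precision

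*Combined protocol and SAP*

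**What the plan says.** Section 14.1, step 4 gives the order: "The patient will be given routine intravenous procedural sedation and one minute prior to the start of the colonoscopy" the nurse delivers the study drug. Glucagon or saline is allocated 1:1 by shuffled cards in envelopes and drawn up "in a covered syringe preventing visualization of syringe content".

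The sedation outcome is item 5 of section 8.2, "Amount of sedatives used", with no agent, unit or time window. Step 5 of section 14.1 has nursing staff record "use of sedatives for the procedure", again without separating doses given before the study drug from doses given after it.

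Section 8.3 plans a matched t-test for continuous variables and names no covariate. Section 16.3 tells patients that with glucagon "the colonoscopy may take less time, require less intravenous sedation and/or find more polyps".

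**The concern.** Sedatives given before the syringe cannot respond to what is in it. Only later doses can carry a pharmacological effect of glucagon on sedation need. Section 9.1 expects such an effect, since it names greater sedative use as one consequence of spasm.

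If the two parts are added and compared as one amount, the first part contributes variation between patients but no treatment signal. A real reduction in sedation during the procedure would then be harder to detect, and a null result could be reported as no effect on something offered to patients as a possible benefit. The pre-drug amount is in effect a baseline value. If it is not written down separately at the time, it may not be recoverable afterwards.

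**Working it through.** **Plan's own figure.** There is none for sedation. The only sample-size calculation (section 10.4) is for cecal intubation time and does not bear on this point.

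**Inputs from the documents.** Enrolment is 200 (section 10.1) with 1:1 allocation (section 14.1, step 1), so about 100 per arm.

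**Assumed inputs.** The documents give no sedative dose, SD or effect. Assume a true effect of 0.40 SD of the post-drug amount, two-sided alpha 0.05 and an independent two-sample t-test. Section 8.3 says matched, but no matching is described.

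**Step 1: bias.** Write total T = P + Q, with P given before and Q after the study drug. Under blinded randomisation P has the same mean in both arms, so the expected difference in T equals that in Q. In a simulation with SD 1 for each part, independence and a true difference of −0.40, the mean difference was −0.40 for both T and Q. The standard error was 0.141 for Q, matching √(2/100), and 0.199 for T, close to √(2 × 2/100) = 0.200. The cost is precision, not bias.

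**Step 2: percentage effect.** That simulation used control means of 3 before and 2 after the drug. A reduction of 0.40 is 0.40/2 = 20% of the post-drug amount but 0.40/5 = 8% of the total.

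**Step 3: power when P and Q are independent.** If P makes up a share s of the variance of T, the standardised effect becomes 0.40 × √(1 − s).

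| Share s | Effect (SD) | Power, 100 per arm |
|---|---|---|
| 0 (same initial dose for all) | 0.400 | 80.4% |
| 0.25 | 0.346 | 68.4% |
| 0.50 | 0.283 | 51.2% |
| 0.75 | 0.200 | 29.1% |

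**Step 4: correlated doses.** Let the SD of Q be 1, the SD of P be k and their correlation r. Then

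- SD of the unadjusted total = √(1 + k² + 2rk)
- residual SD after adjusting for P = √(1 − r²)

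The variances differ by (1 + k² + 2rk) − (1 − r²) = (k + r)², which is never negative. Apart from one degree of freedom, adjustment is therefore never less precise than the unadjusted total.

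| r | k | Power, unadjusted total | Power, adjusted |
|---|---|---|---|
| 0 | 0 | 80% | 80% |
| 0 | 1 | 51% | 80% |
| 0.5 | 1 | 37% | 90% |
| −0.5 | 1 | 80% | 90% |
| −0.5 | 0.5 | 90% | 90% |

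In the last row the slope of Q on P is r/k = −1: each extra unit beforehand is offset by one unit less afterwards, and the total already matches the adjusted analysis.

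**Step 5: total or post-drug amount as outcome.** Since T = P + Q, regressing T on arm and P gives the same arm coefficient and standard error as regressing Q on arm and P. Only the slope on P changes, by exactly 1.

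**The case against.** The strongest reply is that nothing here is invalid. Whole-procedure sedation is what the patient receives, it fits the benefit worded in section 16.3, and randomisation keeps the comparison fair. This stands. A reader might infer that the sedation comparison is biased; step 1 shows that it is not.

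A second reply is that the loss is assumed throughout. The documents do not say whether the initial dose is fixed or titrated, or how later doses are given. This also stands: the loss could be nil, and with offsetting doses the unadjusted total (90%) would beat an unadjusted post-drug amount (about 80%). It does not count against the adjusted analysis, which did at least as well in every case tried.

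A third is that whole-procedure sedation need not be demoted to a descriptive figure. That is right, because after adjustment the two outcomes give the same treatment estimate.

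Two further inferences are tempting. One is that the nursing record already holds the split; section 14.1 describes no timing of doses, so it may not. The other is that early dosing may differ by arm, because a nurse opens the envelope (step 3) before sedation is given (step 4). The documents do not say that this nurse decides the sedation, so this is a possibility and not a finding. A split record would make any such imbalance visible.

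**Conclusion.** The point holds as a cheap gain in precision on a loosely defined outcome. The order in step 4, the undivided amount in aim 5 and step 5, and the absence of a covariate in section 8.3 are all in the text. That the amount covers all doses is the natural reading of an undivided procedure-level record; the plan does not use the word total.

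The size cannot be established. With an assumed effect of 0.40 SD and 100 per arm, power runs from 80% (no loss, fixed initial dose) to about 51% when independent pre-drug doses make up half of the variance of the total. A larger share would cost more. One-for-one offsetting would cost nothing against the adjusted analysis. A demonstrated loss of power is more than the documents support.

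Priority is minor. Sedation is one of 11 aims, and the sample size rests on cecal intubation time.

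**What to change.** In section 14.1, step 5, have nursing staff record the amount of each sedative given before the study-drug injection and the amount given after it, by agent and in that agent's own unit. In section 8.2, state in aim 5 which amount is the outcome. In section 8.3, compare arms on that amount by linear regression with the pre-drug amount of the same agent as covariate. Either the total or the post-drug amount may be the outcome, so the total can stay as the reported figure.

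The cost is one extra recording field and one covariate. If more than one agent is used there will be one estimate per agent, best reported with confidence intervals given the 11 aims. No extra patients or procedures are needed, and sedation practice is unchanged.

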**14.2 Interviews, questionnaires, and/or surveys will be administered or focus groups will be conducted:**

Yes  No

List any standard instruments used for this study:

Please refer to attached Patient and Endoscopist questionnaire. Both questionnaires utilize a visual analog scale to gauge patient and endoscopist response. We will use a 100mm visual analog scale and the distance from the left endpoint will be taken as the response value. This technique has been validated and previously used for endoscopic studies. These forms will be translated into both Spanish and Chinese.

Attach any non-standard instruments at the end of the application.

**14.3 Conduct of study procedures or tests off-site by non-UCSF personnel:**

Yes  No

If yes, explain:

**14.4 Sharing of experimental research test results with subjects or their care providers:**

Yes  No

If yes, explain:

**14.5 \* Specimen collection for future research and/or specimen repository/bank administration:**

Yes  No

**14.6 Time commitment (per visit and in total):**

Potential study subjects will be given enough time to review and ask questions regarding the informed consent form (30 minutes to 1 hr). Actual colonoscopic procedures vary from 30 to 45 minutes. Answering of questionnaires will take approximately 10 to 20 minutes. Total time commitment will range between 70 minutes to 135 minutes.

**14.7 Locations:**

- SFGH Outpatient Endoscopy Unit: The patients will be consented on the day of the procedure. This process will take about 10 additional minutes of time. Longer time will be allotted if the patient requires more time for further explanation.
- The day following the procedure, patients will fill out their questionnaire and mail the responses back using a self-addressed envelope.

**14.8 Describe the resources in place to conduct this study in a way that assures protection of the rights and welfare of participants:**

Approximately ~100-125 patients safely undergo upper endoscopy and colonoscopy at the SFGH endoscopy center per week. Previously established protocols such as secure storage of all patient data, physician-nurse-patient time out, post-procedure recovery protocol and clinic follow-up for all patient necessitating further gastroenterology care already ensures patient privacy and safety. Our study will work within the framework of above stated SFGH endoscopy center protocols and no deviations (apart from study medication administration) have been proposed in our study. Furthermore, [name] and [name], will be present in the SFGH endoscopy center for all potential study cases and will be actively involved in the care of all study participants.

## 15.0 Alternatives

### 15.1 Study drug or treatment is available off-study:

- Yes  
 No  
 Not applicable

### 15.2 \* Is there a standard of care (SOC) or usual care that would be offered to prospective subjects at UCSF (or the study site) if they did not participate:

- Yes  No

If yes, describe the SOC or usual care that patients would receive if they choose not to participate:

If patients choose not to participate they will resume their scheduled procedure as planned.

### 15.3 Describe other alternatives to study participation that are available to prospective subjects:

Since the colonoscopy procedure itself is not different whether a patient participates in the study or not, patients who do not wish to enroll will undergo the same procedure. Furthermore, because the use of glucagon prior to colonoscopy is variable amongst gastroenterologists, a patient not enrolled in the study may still receive glucagon during the colonoscopy.

## 16.0 Risks and Benefits

### 16.1 \* Risks and discomforts:

Previously published research studies on the use of glucagon have noted mild nausea and rarely vomiting as the main side effect experienced with glucagon therapy. The rate of nausea ranges from 4-24% across the studies. Patients will be notified of this risk prior to obtaining informed consent and PRN Zofran will be administered if the patient develops nausea or vomiting. It is important for the CHR to recognize that intravenous glucagon as proposed for this study is routinely use during all ERCP examinations. This has been the case for over 5000 ERCP examinations by [name] for the past 30 years and no adverse reactions been noted over this period of time. Furthermore, some gastroenterologist prescribe glucagon prior to all colonoscopies.

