#### 16.5 Explain why the risks to subjects are reasonable:

Some gastroenterologists prescribe glucagon prior to endoscopy as a routine practice. Thus, patients enrolled in the study are not at a higher risk of complication than the general population since patients outside the study may still receive glucagon prior to their colonoscopy. Furthermore, the only side effect noted with glucagon therapy has been a slightly higher incidence of nausea/vomiting. All cases of nausea/vomiting noted in previous studies were responsive to anti-emetic therapy therefore all patients that develop nausea/vomiting during or after their colonoscopy will be symptomatically treated with intravenous fluids and anti-emetics. The potential benefits that may be derived from glucagon therapy prior to colonoscopy outweigh the slight increase in anti-emetic responsive nausea that may occur with glucagon therapy. Furthermore, we hope to better define the side-effect profile of glucagon prior to colonoscopy with this study by measuring patient blood sugar levels at the end of the colonoscopy.

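### Nausea and vomiting, named as glucagon's main side effect, are not among the listed data items, so no comparison by arm is planned

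*Combined protocol and SAP*

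**What the plan says.** **The harm.** Section 16.1 reports that earlier studies "have noted mild nausea and rarely vomiting as the main side effect experienced with glucagon therapy" and that "The rate of nausea ranges from 4-24% across the studies". It adds that "PRN Zofran will be administered if the patient develops nausea or vomiting". Section 16.2 says fluids and anti-emetics will be at hand. All of this concerns treating nausea, not recording it.

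**The benefit-risk statement.** Section 16.5 argues that "The potential benefits that may be derived from glucagon therapy prior to colonoscopy outweigh the slight increase in anti-emetic responsive nausea". On side effects it says "we hope to better define the side-effect profile of glucagon prior to colonoscopy with this study by measuring patient blood sugar levels"; the measurement is timed to when the procedure finishes. Section 9.1 repeats the intention to measure blood glucose at that time.

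**The data items.**
- Section 8.2 lists eleven aims: three procedure times, adenoma detection, sedative use, three endoscopist gradings, and three patient gradings (pain, fullness, acceptance of a repeat).
- In section 14.1, step 5, nurses record "cecum intubation time, colonoscope withdrawal time, total procedure time, use of sedatives for the procedure". The endoscopist grades difficulty, visualization and spasm, and adenoma detection is taken from pathology.
- In section 14.1, step 7, patients grade pain, fullness and willingness to have another colonoscopy on a mailed form.
- Section 8.3 names tests for continuous and categorical variables and no safety outcome.

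**The concern.** The trial asks whether glucagon should be given routinely before colonoscopy, and its hypothesis in 8.1 includes a better patient experience. A reader deciding on routine use will want the gain in procedure time and comfort set against the extra nausea, from the same randomised patients. The plan's own range for nausea runs from a minor nuisance to about one patient in four, so the size of the harm is not settled.

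Randomisation and blinding are already in place, and they are the costly part of a fair comparison. What is missing is an instruction to write the events down in the same way for every patient. Without it, the report could describe efficacy by arm while its account of the main known side effect rested on whatever was charted.

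**Working it through.** **1. Check of the lists.** I looked for nausea, vomiting, anti-emetic use, any adverse-event item and blood glucose in every place where data are specified.

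- Aims (8.2): none of these. Aim 5 covers sedatives, which are not anti-emetics.
- Nurse, endoscopist and pathology records (14.1, step 5): none.
- Patient gradings (14.1, step 7): none.
- Remaining steps of 14.1 (randomisation, consent, drug preparation, dosing, discharge): none.
- Analysis (8.3): no safety outcome.

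Blood glucose is promised in 9.1 and 16.5 and appears in none of these lists.

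**2. Would recording be informative at the planned size?** The plan has no nausea calculation to reproduce. Its 67 per arm in 10.4 concerns cecal intubation time.

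Inputs:
- 200 patients (10.1, 10.2) at 1:1 (14.1, step 1), so about n = 100 per arm.
- Nausea range of 4-24% (16.1). If this applies to the glucagon arm, it means 4 to 24 cases per 100.
- Placebo rate p0: not given. I assume 1%, 4% or 8%.
- Two-sided alpha 0.05 and 80% power (my choice).

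*Arcsine method.* The detectable rate is p1 = sin²[(φ0 + h)/2], with φ0 = 2·arcsin√p0 and h = (1.960 + 0.842)·√(2/100) = 0.396.
- p0 = 1%: φ0 = 0.200, sum about 0.597, p1 = 8.6%.
- p0 = 4%: φ0 = 0.403, sum 0.799, p1 = 15.1%.
- p0 = 8%: φ0 = 0.574, sum 0.970, p1 = 21.7%.

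*Normal approximation.* Power = Φ[(d − 1.960·se0)/se1], where d = p1 − p0, se0 = √[2·p̄(1 − p̄)/100], p̄ is the mean of the two rates, and se1 = √[(p0(1 − p0) + p1(1 − p1))/100]. Power reaches 80% at p1 = 10.0%, 15.8% and 22.1% respectively.

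The two methods together give about 9-10%, 15-16% and 22%.

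**3. Power for particular pairs** (normal approximation, 100 per arm):
- 4% vs 24%: 0.99.
- 4% vs 14%: 0.70 (0.73 by arcsine).
- 4% vs 10%: se0 = 0.0361, se1 = 0.0358, so Φ[(0.060 − 0.0707)/0.0358] = 0.38.
- 4% vs 8%: 0.22.
- 1% vs 4%: 0.27.

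**4. Precision.** The Wald 95% half-width is 1.96·se1:
- 4% vs 24%: 9.2 points, so a 20-point difference has an interval of about 11 to 29.
- 4% vs 14%: 7.8 points, so a 10-point difference has an interval of about 2 to 18.
- 4% vs 10%: 7.0 points, so a 6-point difference has an interval of about −1 to 13.

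**5. If only 67 per arm are enrolled,** the normal approximation gives detectable rates of 13.5% against 1% and 19.5% against 4%.

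**The case against.** Five points can be made on the other side.

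- *The benefit-risk sentence is not a study question.* This stands. A reader might infer that the trial sets out to show benefit outweighing harm and has left itself unable to. The sentence in 16.5 answers the ethics form's question on why the risks are reasonable, and it leans on earlier studies. It is neither the hypothesis in 8.1 nor an aim in 8.2.
- *The plan does not promise a full side-effect profile.* This also stands. Cut short, the sentence in 16.5 reads like a general undertaking, but it is limited to blood sugar, and 16.1 makes no such undertaking. The inconsistency the text supports is narrower: the promised glucose measurement is missing from the aims and steps.
- *There may be some data.* Section 18.1 names the outpatient or hospital chart as a source, and an anti-emetic given on site would probably be charted. So a reader should not conclude that the trial will have no nausea data. But no extraction is specified, charting would vary, and symptoms after discharge would be missed.
- *The questionnaires are attachments that could not be read.* A nausea item on them cannot be excluded. Step 7 names the items patients grade, though, and nausea is not one. If the form does include it, the aims and procedures should say so.
- *The harm is mild and the trial is small.* Sections 16.1 and 16.5 describe mild, treatable nausea and a slight increase. An increase of a few points would remain unresolved at 100 per arm. That limits what the addition can show, but an interval that rules out a large excess is still useful.

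**Conclusion.** The point holds as a gap in planned data capture. The listed aims, data steps and analysis contain no nausea, vomiting or anti-emetic item, although 16.1 calls this the main side effect, and the promised blood glucose measurement is not carried into the aims or procedures. No stated aim or efficacy comparison is damaged. What is lost is a systematic blinded comparison of the main known harm.

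At about 100 per arm, a nausea rate near the top of the quoted range would very probably be detected against a low placebo rate, and small increases would not be. Those figures rest on assumed placebo rates and on reading the 4-24% range as applying to glucagon-treated patients, which the plan implies but does not state. This is a worthwhile, inexpensive improvement and not a flaw that invalidates the trial.

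**What to change.** Add to 8.2, and to 14.1 steps 5 and 7:

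- a nurse record, completed before discharge for every patient, of nausea (yes/no), vomiting (yes/no) and any anti-emetic given;
- one nausea item on the next-day patient form.

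In 8.3, pre-specify nausea and vomiting as a safety outcome, reported by arm as a risk difference with a 95% confidence interval. Report how many mailed forms were returned in each arm. Treat the pre-discharge record as the main source, because it does not depend on the post.

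List the end-of-procedure blood glucose measurement promised in 9.1 and 16.5 in the aims and in the procedure steps.

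The cost is slightly longer forms, translation of one added patient item, and one more table. The mailed item will have some non-response. No extra patients or visits are needed, and nothing about treatment changes.
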